8.1 Extent of exposure

The following descriptive summaries will be generated using the SS by first dose received:

- a) Study IMP duration (weeks) by first dose received, calculated as follow:

$$\text{Study IMP duration (weeks)} = \frac{\text{Date of last dose} - \text{Date of first dose} + 1}{7}$$

- b) Cumulative study IMP Duration using > 0 weeks, ≥ 6 weeks, ≥ 12 weeks, ≥ 18 weeks, ≥ 24 weeks, ≥ 30 weeks, ≥ 36 weeks, ≥ 42 weeks and ≥ 48 weeks and 52 weeks;
- c) Number of Infusions Received as continuous and using the following categorical values: 1-6, 7-12, 13-18, 19-24, 25-30, 31-36, 37-42, 43-48, and 49-52.

The number of participants with dose change at each visit will be summarized using the SS by the most recent dose received.

All IMP administration details will be listed.

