3 DATA ANALYSIS CONSIDERATIONS

3.1 General presentation of summaries and analyses

Statistical analysis and generation of tables, figures, participant data listings, and statistical output will be performed using SAS[®] Version 9.3 or higher. All tables and listings will use Courier New font size 9.

Descriptive statistics will be displayed to provide an overview of the study results. For continuous variables, descriptive statistics will include number of participants with available measurements (n), mean, standard deviation (SD), median, minimum, and maximum.

For categorical variables, the number and percentage of participants in each category will be presented. Unless otherwise noted, the denominator for percentages will be based on the number of participants included in the respective analysis set. Participants with missing data can generally be accounted for using the following approaches:

- For summaries of demographics and Baseline characteristics: summarize percentages based on all participants in the analysis set and include a “Missing” category (corresponding to participants with missing data for the variable being summarized) as the last row in the list of categories being summarized.
- For summaries of efficacy and safety endpoints, unless otherwise specified: summarize percentages based only on those participants with observed data for the variable being summarized. As the denominator may be different from the number of participants in the analysis set being considered, the denominator should be displayed in the table. The general format for displaying this will be “n/Nsub (%)”.

Unless otherwise noted, all percentages will be displayed to one decimal place. No percentage will be displayed for zero counts, and no decimal will be presented when the percentage is 100%.

For PK concentration data, summary statistics will include geometric mean, geometric coefficient of variation (geoCV), 95% confidence intervals (CIs) for geometric mean, arithmetic mean, SD, median, minimum, and maximum.

Decimal places for descriptive statistics will always apply the following rules:

- “n” will be an integer;
- Mean (arithmetic, geometric), SD, and median will use one additional decimal place compared to the original data;
- geometric CV [%] will be presented with one decimal place;
- Minimum and maximum will have the same number of decimal places as the original value.

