3.6 Treatment assignment and treatment groups

For the analyses using SS by the first dose received, study participants will be grouped according to the dose levels of IMP participants first received [REDACTED] in this study (i.e. before any switching occurs) using the exposure data from CRF. For example, if study participants randomized to IMP [REDACTED] and first received IMP [REDACTED], then these study participants will be allocated to IMP [REDACTED]. If a study participant first received IMP [REDACTED] and then switched to [REDACTED], then the study participant will be allocated to [REDACTED].

For the analyses using SS by the most recent dose received, study participants will be grouped according to the most recent dose level of IMP participants received prior to each visit or the onset of events using the exposure data from CRF. For example, if a study participant first received IMP [REDACTED] and then switched to [REDACTED] prior to Visit 5, then the participant will be allocated to [REDACTED] at Visit 5.

For the efficacy analyses using SS by dose switch during the Treatment Period, study participants will be grouped into dose adjuster or dose non-adjuster. A study participant who receive different dose during the Treatment Period from the randomized dose level will be classified as a dose adjuster, otherwise dose non-adjuster. For example, if a study participant was randomized to and first received IMP [REDACTED] and then switched to [REDACTED], then the study participant will be allocated to dose adjuster.

For the analyses using RS, study participants will be grouped according to the dose levels of IMP to which study participants were randomized.

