8 SAFETY ANALYSES

All safety analyses will be presented using the SS. Listings will be presented by treatment group and participant; tabulations will be presented by treatment group. Unless otherwise specified, safety analyses will be presented by the most recent dose the study participants received in MG0004 as described in [Section 3.6](#).

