- **Treatment Period:** a TEAE will be assigned to the Treatment Period if the start date of the event is on or after the date of the first administration of MG0004 IMP on Day 1, up to 7 days after the last dose of IMP;
- **Observation Period:** a TEAE will be assigned to the Observation Period if the start date of the event is greater than the day after Treatment Period until 8 weeks following the final dose; events starting later than 8 weeks following the final dose of IMP are not considered TEAEs.

A TEAE will be counted as a TEAE related to IMP if the response to the question “Relationship to Study Medication” is “Related”.

AEs will be presented as “number of participants (percentage of participants) [number of events]”. In this style of output, “[number of events]” will include all cases of an AE including repeat occurrences in individual participants, while “number of participants” will count each participant only once.

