8.2.2 Adverse events summaries

TEAEs will be summarized by the most recent dose level prior to onset of TEAEs and RLZ total, including the number and percentage of study participants and frequency. Additional details are described below:

1. Overview of TEAEs will include following categories: any TEAEs, serious TEAEs, participant discontinuation due to TEAEs, permanent withdrawal of IMP due to TEAEs,

temporary withdrawal of IMP due to TEAEs, TEAEs requiring dose change, treatment-related TEAEs, severe TEAEs, TEAEs leading to death, all deaths (AEs leading to death).

2. Incidence of TEAEs will be summarized by SOC, HLT, PT for:

- Any TEAEs
- Any TEAEs during Treatment Period
- Any TEAEs by maximum intensity (mild, moderate and severe)
- Any TEAEs by relationship
- Severe TEAEs
- Non-serious TEAEs above reporting threshold of 5% of study participants
- Fatal TEAEs
- Fatal TEAEs by relationship
- Serious TEAEs
- Serious TEAEs by relationship
- Participant discontinuation due to TEAEs
- TEAEs leading to permanent withdrawal of IMP
- TEAEs leading to temporary withdrawal of IMP
- TEAEs requiring dose change
- Treatment-emergent AESM
- Treatment-emergent AESI

3. Incidence of any TEAEs will be summarized by decreasing frequency of PT.

AESMs include severe headache, severe GI disorders (i.e., abdominal pain, diarrhea, vomiting), and opportunistic infection.

AESIs are the cases of potential Hy's Law (see [Section 8.3.1](#)).

AESMs and AESIs will be identified based on the assessment by the Investigator as recorded in the CRF. An AE will be counted as an AESM if there is a 'yes' response to the question "Adverse event of Special Monitoring?" and 'no' otherwise. An AE will be counted as an AESI if there is a 'yes' response to the question "Adverse Event of Special Interest?" and 'no' otherwise.

When applicable adverse event summaries will be ordered by alphabetical SOC, alphabetical HLT within SOC and decreasing frequency of PT in the RLZ total column for tables.

Listings of all TEAEs, all non-serious TEAEs, serious TEAEs, permanent withdrawal of IMP due to AEs, study participant discontinuation from study due to AEs, AEs leading to death, AESIs, AESMs will be presented by treatment group and participant. Persistent AEs and TEAE will be flagged in the listings. Most recent dose will be presented in listing even when the AE start date is partial.

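### After a dose switch, no exposure table matches the by-dose TEAE columns, and the participant denominator for those columns is not defined

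*SAP*

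**What the plan says.** SAP 8 sets a default: unless otherwise specified, "safety analyses will be presented by the most recent dose the study participants received in MG0004". SAP 8.2.2 applies it to the primary endpoint: "TEAEs will be summarized by the most recent dose level prior to onset of TEAEs and RLZ total". SAP 8.2.3 does the same for adverse events of focus.

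SAP 8.1 is the exception. For IMP duration, cumulative duration and number of infusions it says "The following descriptive summaries will be generated using the SS by first dose received". The only item there by most recent dose is a count of dose changes at each visit. Administration details are listed, not summarised.

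SAP 3.6 defines the most-recent-dose grouping through the "most recent dose level of IMP participants received prior to each visit or the onset of events". On denominators, SAP 3.1 has a general rule ("the denominator for percentages will be based on the number of participants included in the respective analysis set") and a rule for efficacy and safety endpoints ("summarize percentages based only on those participants with observed data for the variable being summarized"). Neither mentions participants who received both doses. SAP 8.2.1 requires each adverse event row to show participants, a percentage and an event count.

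The protocol plans all safety summaries by first dose received (section 3, Estimands; section 9.2). SAP 3.9, which lists departures from the protocol, does not mention the move to most recent dose.

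**The concern.** The Estimands text in protocol section 3 gives the primary aim as comparing the long-term safety of two dose levels. Protocol 6.6 allows switching after the first dose for tolerability, efficacy or bodyweight reasons. A participant who moves from dose A to dose B at Week 6 then contributes later TEAEs to column B, while the whole treatment duration is credited to A. Anyone who reads the TEAE table beside the exposure table is comparing events from one set of person-time with exposure from another.

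The percentage has a separate gap. The grouping rule attaches a participant to a dose at a visit or at an event onset. Someone with no event has no onset, so the rule does not say in which column, or columns, that person counts in the denominator. At least three readings are open: the first-dose N, everyone who ever received the dose, or the whole Safety Set. Two programmers following the SAP could report different by-dose percentages for the primary endpoint.

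**Working it through.** The documents give no sample size calculation, switch rate or event rate on this point, so there is no stated figure to reproduce. What follows illustrates size only.

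**Inputs.** From the documents: 52-week Treatment Period (SAP 3.2.2); 1:1 allocation (SAP 2.3); 6 weeks as the period for which the randomised dose should be kept where possible (protocol 6.6). Assumed: 100 per arm (the ratios do not depend on arm size; SAP 3.9 caps the study at 240, or 120 per arm), everyone treated for 52 weeks, a constant and equal event rate on both doses, one switch per switcher, and the switch proportions. Only the Treatment Period is counted.

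**Person-time.** Let pA and pB be the proportions leaving A and B at week s.

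- Weeks on A = 5200 − 100·pA·(52 − s) + 100·pB·(52 − s)
- Weeks on B = 5200 + 100·pA·(52 − s) − 100·pB·(52 − s)

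First-dose exposure is 100 × 52 = 5200 for each arm whatever happens later. With equal true rates, events by dose at onset are proportional to weeks on dose. Dividing both columns by 5200 therefore gives an apparent B:A rate ratio of (weeks on B)/(weeks on A). The true ratio is 1.00.

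| pA, pB | s | Weeks on A | Weeks on B | Apparent ratio | Ever on A / B |
|---|---|---|---|---|---|
| 0.3, 0 | 6 | 5200 − 1380 = 3820 | 6580 | 1.72 | 100 / 130 |
| 0.3, 0 | 26 | 5200 − 780 = 4420 | 5980 | 1.35 | 100 / 130 |
| 0.2, 0 | 6 | 5200 − 920 = 4280 | 6120 | 1.43 | 100 / 120 |
| 0.3, 0.2 | 6 | 5200 − 460 = 4740 | 5660 | 1.19 | 120 / 130 |
| 0.2, 0.2 | 6 | 5200 | 5200 | 1.00 | 120 / 120 |

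In the last row person-time balances, but 120 participants have been on each dose against a first-dose N of 100, so the choice of denominator still matters.

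**Percentages.** Take the first row and assume one event per participant-year. The chance of at least one event in t weeks is 1 − exp(−t/52).

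- Column A: 70 × 0.632 + 30 × 0.109 = 47.5 participants
- Column B: 100 × 0.632 + 30 × 0.587 = 80.8 participants

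| Denominator | A | B |
|---|---|---|
| First-dose N (100, 100) | 47.5% | 80.8% |
| Ever received (100, 130) | 47.5% | 62.2% |
| Whole Safety Set (200, 200) | 23.8% | 40.4% |

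All three differ between doses although the true rates are equal. The ever-received N counts the right people, but their time at risk is still unequal. Only events divided by time on the dose recover equality.

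**The case against.** A reader might infer that the SAP divides by-dose TEAE counts by the first-dose N. It does not say so. The denominator is left open, SAP 3.1 asks for it to be displayed where it may differ from the analysis-set N, and table shells (mentioned in SAP 14.1 but not among these documents) may settle it. That stands: a wrong percentage is a possible result, not a stated rule.

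A reader might also treat 1.72 as a bias in a planned estimate. No exposure-adjusted rate, rate ratio or test is planned, and the exposure table is labelled by first dose. The ratio arises only when the two tables are read together. This stands as well.

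The illustration is near the severe end. It assumes one-way switching, early switches and full follow-up, whereas SAP 2.3 has participants leaving for MG0007 after as few as 6 visits. If treatment ended at Week 12 with 30% switching at Week 6, the ratio would be (1200 + 180)/(1200 − 180) = 1.35. Protocol 4.2 describes switching in both directions, for TEAEs and for worsening, so imbalance cannot be taken as expected. One-way transfer would follow if a dose were dropped after the MG0003 interim analysis (SAP 2.3), but the documents do not say that this occurred.

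Nor is it true that the plan has no per-dose counts other than by first dose. Vital signs are taken at each weekly visit and tabulated by visit and most recent dose with n shown (SAP 8.4.1), which approximates participant-weeks by dose. A reader would have to assemble this from many visit rows, and it yields neither infusions nor the number ever on a dose.

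Finally, SAP 8.1 is the section that follows the protocol's first-dose grouping; the TEAE tables depart from it. This affects where the remedy goes but leaves the mismatch in place.

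**Conclusion.** The point holds in limited form. Followed exactly, the SAP produces by-dose TEAE tables and exposure tables that describe different person-time once anyone switches, and it does not define the N behind the by-dose TEAE percentages. The RLZ total column is sound. What is affected is the dose comparison of the primary safety endpoints, and the same pairing recurs in the Japan-only tables (SAP 11.2).

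The size cannot be stated from the documents. Under the assumptions above, the apparent ratio at equal true rates runs from 1.00 with balanced switching to 1.72 with 30% one-way switching at Week 6. These figures show what the mismatch could do and do not predict what it will do. The gap merits correction before the tables are produced because the remedy is small and the affected tables carry the primary objective.

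**What to change.** - **SAP 8.1:** add, for each dose level, the number of participants who ever received it, the infusions given at it, and the participant-weeks on it. Assign each interval to the most recent dose as in SAP 3.6, and the post-dose TEAE window (as far as observed) to the last dose.
- **SAP 8.2.2, 8.2.3 and the matching tables in 11.2:** use everyone who ever received the dose as the column N, show participant-time in the header, and footnote that switchers count in both columns.
- **Primary TEAE rows:** add events per participant-time, because ever-received percentages still reflect unequal time at risk.
- **Grouping:** also give the primary TEAE tables by first dose received, as protocol section 3 states, or record the change of grouping in SAP 3.9. First-dose exposure then sits beside first-dose TEAE tables.

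The cost is SAP wording, one derivation from exposure data that SAP 3.6 already uses, and a few more table columns or repeats. The by-dose columns will sum to more than the Safety Set N, which the footnote explains. Nothing changes in study conduct or data collection.

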Recording of AEs		X	X	X	X	X	X	X	X	X	X	X	X
Blood sampling for PK ⁿ		X		X								X	
Blood sampling for ADA		X		X				X ^o				X	X
Blood sampling for IgG and IgG subclasses ^p		X	X	X		X		X		X		X	X
Blood sampling for IgA, IgM, IgE		X						X ^q				X ^r	X
Blood sampling for exploratory safety biomarker analysis ^s			X										
MG-specific autoantibodies		X		X				X ^o				X	X
Serum complement levels (C3,C4) and cytokines ^t			X					X					
Plasma complement levels (C3a and C5a) ^t			X					X					

Table 1-1: Schedule of activities

	Week	Weeks 1-4		Weeks 5-8				Weeks 9-48 ^a		Weeks 49-51		Week 52	Week 60
	Visit ^b	1 (Screening /Baseline) ^c	2-4	5	6	7	8	1 st visit	2 nd , 3 rd , and 4 th visits	49	50 51	52 or PEOT	53 EOS
Assessments	Visit type	S	S	S	H	S	H	S	H	S	H	S	S

ADA=anti-drug antibody; ADL=activities of daily living; AE=adverse event; AESM=adverse events of special monitoring; C-SSRS= Columbia Suicide Severity Rating Scale; ECG=electrocardiogram; EOS=End of Study; EQ-5D-5L=5-level European quality of life 5 dimension; GI=gastrointestinal; H=home visit; HIV=human immunodeficiency virus; Ig=immunoglobulin; IGRA=interferon gamma release assay; IMP=investigational medicinal product; INR=international normalized ratio; IRT=interactive response technology; MG=myasthenia gravis; MGII=myasthenia gravis impairment index; MG-ADL=myasthenia gravis-activities of daily living; MGFA=Myasthenia Gravis Foundation of America; MGQoL15r=revised 15-item myasthenia gravis quality of life questionnaire; PEOT=premature end of treatment; PK=pharmacokinetic(s); PRO=patient-reported outcome; PTT=partial thromboplastin time; QMG=quantitative myasthenia gravis test; S=site visit

^a From Weeks 9 to 48, the schedule will operate on recurring 4-week cycles wherein the first visit of each 4 weeks will be site visits and the subsequent 3 visits (2nd, 3rd, and 4th visits) will be home visits. Accordingly, Visits 9, 13, 17, 21, 25, 29, 33, 37, 41, and 45 will be site visits and the remaining visits will be home visits. At the discretion of the Investigator, home visits may be changed to site visits. Study participants may also choose to complete the visits at the site on the scheduled home visits.

^b Visit windows of ±2 days are allowed for all visits.

^c For any study participant who enrolls in MG0004, the final visit in MG0003 (Visit 14) or MGC003 (Visit 14) will serve as Visit 1 in MG0004. All activities should be completed at Visit 1 (±1 week).

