^d For criteria pertaining to laboratory measures, the last available value from MG0003 or MGC003 will be used for evaluation of study participant eligibility, as long as the measurement was taken within the last 4 weeks (not older than 32 days) prior to MG0004 screening.

^e To be collected four times during the study: Screening/Baseline, 1 Week 25 (site visit), Week 52 (or PEOT), and EOS Visit.

^f A full Columbia-Suicide Severity Rating Scale (C-SSRS) assessment will be performed only when study participant has a positive response to Question 1 of the suicidal ideation query. If a study participant has active suicidal ideation as confirmed by the answer “Yes” to Question 4 or Question 5 of the C-SSRS assessments, the study participant will be excluded or withdrawn from the study and immediately referred to a mental healthcare professional. Complete C-SSRS will observe the “since last visit” version recorded at Visit 14 in MG0003 or MGC003.

^g MGII is optional for all study participants.

^h From Weeks 9 to 48, an ECG will be performed every 3 months (ie, Weeks 9, 21, 33, and 45).

ⁱ Urine pregnancy test will be performed using a dipstick test; a positive urine pregnancy test must be confirmed using a serum pregnancy test.

^j Every 6 months.

^k From Weeks 9 to 48, the tuberculosis questionnaire will be performed every 3 months (ie, Weeks 9, 21, 33, and 45).

- ^l Study participants must be observed at site postdose for at least 4 hours following the first 2 infusions, and then 2 hours thereafter for subsequent infusions until Week 7, where the participant can be observed for 1 hour at the Investigator's discretion.
- ^m No IMP administration will occur during the PEOT visit for study participants who withdraw from the study or discontinue IMP.
- ⁿ PK samples should be taken predose for all study participants.
- ^o From Weeks 9 to 48, ADA- and MG-specific autoantibodies will be measured every 3 months (ie, Weeks 9, 21, 33, and 45).
- ^p Total IgG will be assessed at all scheduled onsite visits; IgG subclasses will be assessed at Visit 1 and every 3 months thereafter.
- ^q From Weeks 9 to 48, blood sampling for IgA, IgE and IgM will be measured every 3 months (ie, Weeks 9, 21, 33, and 45).
- ^r To be performed only in the event of a PEOT Visit.

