- Bodyweight \geq 100kg: dose to be administered [REDACTED]

If one of the doses described above is determined to be futile and is discontinued after the interim analysis in MG0003 or MGC003, then that dose arm will be dropped from MG0004 as well, and study participants in the affected dose arm will be transferred to the continuing dose arm. If both dose arms are used in MG0004, study participants will be allowed to switch dose arms for tolerability and efficacy reasons at the discretion of the Investigator (see Section 6.6).

In MG0004, rozanolixizumab will be administered SC on a [REDACTED] basis over a 52-week Treatment Period. Weekly visits will be either on-site or at home, as described in the Schedule of Activities (Section 1.3). During the first 4 weeks, the weekly visits will be on-site. From Weeks 5 to 8, on-site visits and at home visits will occur on an alternating basis. From Weeks 9 to 48, study participants will have 1 site visit every 4 weeks, such that 1 site visit will be followed by 3 home visits, unless the study participant chooses to complete the scheduled at-home assessments at the site. Weeks 49 to 51 will then involve 1 site visit followed by 2 home visits. At the end of the 52-week Treatment Period in MG0004, study participants will participate in an 8-week Observation Period.

In exceptional circumstances (eg, pandemic, hurricanes, etc) where study-specific investigations may not be conducted according to study protocol, contingency measures will be in place (see Section 8).

This OLE study will be replaced by MG0007, an OLE study with [REDACTED] based on MG worsening. Upon study site approval of MG0007, as well as fulfilment of regulatory requirements, study participants will have the opportunity to rollover directly into MG0007 and will no longer have the opportunity to rollover to MG0004. In the event a study participant has

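### The SAP's IMP duration formula gives 51.14 weeks for an on-schedule full course, so the 52-week exposure row omits on-time full-course participants (minor)

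*SAP*

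**What the plan says.** SAP 8.1 (Extent of exposure) introduces the variable as "Study IMP duration (weeks) by first dose received, calculated as follow" and sets it to the date of last dose minus the date of first dose, plus one day, divided by seven. Nothing is added for the period covered by the last dose. The cumulative table starts above 0 weeks, rises in 6-week steps and ends with "≥ 42 weeks and ≥ 48 weeks and 52 weeks". The last entry has no operator. The same section bands the number of infusions, ending with "37-42, 43-48, and 49-52". SAP 11.2 repeats the duration and infusion summaries for participants in Japan.

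Protocol 1.3 numbers visits by week. For Weeks 9 to 48 footnote a says: "Accordingly, Visits 9, 13, 17, 21, 25, 29, 33, 37, 41, and 45 will be site visits". Visit 52 is headed Week 52. Footnote b adds: "Visit windows of ±2 days are allowed for all visits". Protocol 4.1 describes the visits as weekly, for example: "During the first 4 weeks, the weekly visits will be on-site".

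For other purposes the SAP uses a different convention. SAP 6.4.2 (concomitant medications) and SAP 8.2.1 (TEAEs) both run the Treatment Period to 7 days after the last dose.

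**The concern.** The formula counts elapsed days from first to last dose, whereas the row label counts treatment weeks. With weekly dosing, 52 doses are separated by only 51 intervals, so the formula falls short of 52 by just under a week.

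The study's primary objective is long-term safety over a 52-week Treatment Period. A reader will take the top row as the number exposed for the planned course. As specified, that row could be empty or nearly so even with perfect adherence, and anyone in it would be there because dosing ran late. A programmer must also guess whether the missing operator means equal to 52 or at least 52.

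The offset affects the low end too. A participant who moves to MG0007 after the minimum of six visits, having had six on-time weekly doses, falls below the 6-week cut-point.

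**Working it through.** **Inputs**

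- Formula: (last dose date − first dose date + 1)/7, from SAP 8.1.
- Visit number equals week number, Visits 1 to 52, from Protocol 1.3.
- Interval between visits: 7 days, from Protocol 4.1.
- Window: ±2 days, from Protocol 1.3 footnote b.
- Assumption: one dose at each of Visits 1 to 52. The frequency is redacted. Weekly dosing is inferred from the weekly visits and from an infusion count that tops out at 52 over 52 weeks. For Visit 52 itself, footnote m says: "No IMP administration will occur during the PEOT visit for study participants who withdraw from the study or discontinue IMP". This withholds the dose only at a PEOT visit after withdrawal or discontinuation, which implies that completers are dosed at Visit 52.

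**Formula for k on-schedule weekly doses**

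- Span = (k − 1) × 7 days.
- As written (+1): duration = [(k − 1) × 7 + 1]/7 = k − 6/7 weeks.
- With the dosing interval credited (+7): duration = [(k − 1) × 7 + 7]/7 = k weeks.

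**Results**

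| Case | Span, days | As written (+1) | With +7 |
|---|---|---|---|
| 6 doses, on schedule | 35 | 36/7 = 5.14 | 42/7 = 6.00 |
| 48 doses, on schedule | 329 | 330/7 = 47.14 | 336/7 = 48.00 |
| 52 doses, on schedule | 357 | 358/7 = 51.14 | 364/7 = 52.00 |
| 52 doses, last 2 days late | 359 | 360/7 = 51.43 | 366/7 = 52.29 |
| 52 doses, last 2 days early | 355 | 356/7 = 50.86 | 362/7 = 51.71 |
| Last dose at Visit 51, on schedule | 350 | 351/7 = 50.14 | 357/7 = 51.00 |
| Last dose at Visit 51, 2 days late | 352 | 353/7 = 50.43 | 359/7 = 51.29 |

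The plan's figure of 52 weeks is therefore not reproduced by its own formula. Reaching 52.0 as written needs a span of 52 × 7 − 1 = 363 days, which is 363 − 357 = 6 days over schedule. Even a first dose 2 days early and a last dose 2 days late give only 362/7 = 51.71.

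**Readings of the row**

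- Equal to 52 requires a span of exactly 363 days.
- At least 52 requires 363 days or more.
- Rounding does not help. SAP 3.1 governs displayed decimals only, and 51.14 and 51.43 both round to 51.

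**Thresholds for the fix**

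A full course with the last dose at the early edge of its window gives 362 days under +7, or 356 days under +1. Either value separates it from a last dose at Visit 51 taken 2 days late (359 or 353 days).

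**The case against.** The strongest reply is that little depends on this row. SAP 8.1 also summarises duration as a continuous variable, bands the infusion count and lists every administration. SAP 5.1 counts participants at each visit. An on-time full-course participant still appears in the 48-week row and in the 49–52 infusion band. All of that stands, and it is why the point is minor.

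A second reply is that elapsed first-to-last-dose time is a legitimate scale, so the lower rows are not wrong in themselves. That is fair, but it does not rescue a top row set at a value that the scale does not reach on schedule. It also means that the offset should be handled for all rows together.

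Three stronger readings are tempting but not supported.

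- **A reader might infer that the row counts participants who received every dose.** It does not. Protocol 6.5.3 allows IMP to be paused after rescue therapy, and Protocol 7.1.4 permits no make-up doses. A long span can therefore contain missed doses, and the infusion count is the plan's measure of receipt.
- **A reader might infer that the Visit 1 allowance (footnote c: "All activities should be completed at Visit 1", within one week either way) lets the first dose move 7 days early while Visit 52 stays fixed, giving 365/7 = 52.14.** The footnote does not say that later visits keep dates independent of the first dose. SAP 3.2.1.1 counts study days from the first infusion, and SAP 6.4.2 and 8.2.1 call the first administration Day 1.
- **A reader might infer that the study's account of long-term safety is distorted.** No endpoint or TEAE incidence uses this duration variable.

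**Conclusion.** The top row is wrong as written, and the point is minor. An on-schedule full course is 6 days (0.86 week) short of 52 weeks under the SAP 8.1 formula, and no reading of the missing operator captures it. Every other row carries the same 6-day offset. The effect is limited to the descriptive exposure table and its Japan-only repeat.

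The conclusion assumes weekly dosing at Visits 1 to 52. If the last scheduled dose were at Visit 51, the shortfall as written would be larger (50.14 weeks). The number of participants affected cannot be derived from the documents, partly because transfer to MG0007 limits how many can reach Week 52.

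**What to change.** In SAP 8.1:

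1. Credit the 7-day dosing interval after the last dose by replacing +1 with +7. This matches the 7-day rule already in SAP 6.4.2 and 8.2.1 and puts all rows on one scale: k on-schedule weekly doses give k weeks, and a full course gives 52.00.
2. Give the top row an operator and the visit window: ≥ 52 weeks, allowing the −2-day window, that is ≥ 362 days.
3. Footnote that the row measures first-to-last-dose span and that receipt of all 52 doses is shown by the infusion-count summary.

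If +1 has to stay for consistency with pooled studies (SAP 4.4 foresees pooling of safety data), label the top row by its day count (≥ 356 days), footnote the 6-day offset for all rows, and keep the note in item 3.

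The cost is one derivation line and a footnote, with no new data. Under +7 every reported duration rises by 6/7 week, and the top row carries a 2-day tolerance that its label must state. That tolerance assumes days are counted from the first infusion. If later visits instead kept nominal dates, a first dose 2 days late with a last dose 2 days early would give 353 + 7 = 360 days and fall just outside it.
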